1.1 Study Objectives

Primary Study Objective

The primary study objective is to demonstrate superiority of VIVITY over SYMFONY or over AT LARA for the proportion of subjects responding “not bothered at all” by halos on the QUVID questionnaire (Q2.3) at 3 months post bilateral implantation.

Secondary Study Objectives

The secondary study objectives are:

- To demonstrate superiority of VIVITY over SYMFONY or over AT LARA for the proportion of subjects responding “not bothered at all” by glare on the QUVID questionnaire (Q3.3) at 3 months post bilateral implantation.
- To demonstrate superiority of VIVITY over SYMFONY or over AT LARA for the proportion of subjects responding “not bothered at all” by starbursts on the QUVID questionnaire (Q1.3) at 3 months post bilateral implantation.

Safety Objective

The safety objective is to assess safety parameters out to 6 months post bilateral implantation.

1.2 Study Description

This is a post-market, prospective, multi-center, randomized, parallel group, controlled, assessor and subject-masked, bilateral implant study. Eligible subjects will be randomly assigned in a 1:1:1 ratio to receive either VIVITY Extended Vision IOL Model DFT015 (test article) or TECNIS SYMFONY Extended Range of Vision IOL Model ZXR00 (control article), or AT LARA extended depth of focus IOL Model 829MP (control article) in both eyes. Subjects and site assessors will be masked to subject treatment assignment until the end of the study.

The schedule of visits is included as Figure 1-1 below and Table 10-1 in the appendix.

[REDACTED]

Approximately 218 bilaterally implanted subjects will be enrolled (consented) at up to 14 sites in Australia and New Zealand to achieve 180 subjects who complete the study, with a target of 9-24 subjects enrolled per site. Site-specific targets may vary based upon individual site capabilities. Estimated time needed to recruit subjects for the study is approximately 6 months.

[figure not shown]
The planned number of evaluable completed subjects per each treatment group is:

- 60 Bilateral VIVITY
- 60 Bilateral SYMFONY
- 60 Bilateral AT LARA

[REDACTED]

The study design is illustrated in Figure 1-1 of the study protocol as follows:

Figure 1–1 Study Design Diagram

1.3 Randomization

Subjects will be randomized in a 1:1:1 ratio to receive treatment with the VIVITY or the SYMFONY or the AT LARA IOLs, respectively. Randomization will be stratified by site.

Only after signing the ICF, will a subject be assigned a subject number by the electronic data capture (EDC) system. If all eligibility criteria are met and the subject desires to continue in the study, randomization will proceed.

No sooner than 10 business days of Visit 00, each eligible subject will be randomized to one of the treatment arms. Subjects will be assigned treatment according to the randomization list

contained within the EDC system and the corresponding treatment assignment will be communicated to the unmasked site user.

1.4 Masking

This study is effectiveness assessor and subject masked. Subjects will be randomized for bilateral implantation with one of the three studied IOLs. The effectiveness assessor and subject masking will be maintained throughout the conduct of the study until all study data is validated and final database lock occurs. [REDACTED]

[REDACTED]

[REDACTED]

[REDACTED]

2 Analysis Sets

2.1 Efficacy Analysis Sets

The primary analysis set for effectiveness analyses will be the All-Implanted Analysis Set (AAS). AAS includes all randomized eyes with successful study IOL implantation.

[REDACTED]

[REDACTED]

- | [REDACTED]
- | [REDACTED]
- | [REDACTED]

[REDACTED]

All effectiveness analyses will be conducted according to actual IOL implanted.

[REDACTED]

[REDACTED]

[REDACTED]

[REDACTED]

- [REDACTED]
- [REDACTED]
- [REDACTED]
- [REDACTED]
- [REDACTED]

[REDACTED]

[REDACTED]

[REDACTED]

[REDACTED]

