8 STUDY POPULATION

The study population consists of male and female subjects (age 22 years and older) with a diagnosis of cataract requiring extraction. Approximately 218 subjects will be enrolled (consented) at up to 14 sites in Australia and New Zealand, with a target of 9-24 subjects per site. Site-specific targets may vary based upon individual site capabilities. Estimated time needed to recruit subjects for the study is approximately 6 months.

It is expected that at least 198 subjects will be randomized and at least 180 subjects will complete the study as follows:

- 60 bilaterally implanted with VIVITY
- 60 bilaterally implanted with SYMFONY
- 60 bilaterally implanted with AT LARA

This accounts for a 10% screen failure rate and a 10% rate of subjects who are not bilaterally implanted with the study IOLs or are lost to follow-up.

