9.3 Treatment Administration

Subjects will be randomized to treatment group prior to surgery, no sooner than 10 business days prior to Visit 00. The lens to which the subject is randomized, must be implanted in both eyes. [REDACTED]

[REDACTED]

Each study surgeon will follow his/her **routine** cataract procedure for all study surgeries. It is permitted to have 1 study-trained surgeon at each site perform IOL implantations. For surgeons with experience prior to the start of the trial, femtosecond laser-assisted cataract surgery (FLACS) is permitted, however it is **NOT** required. The laser may **ONLY** be used for the following:

- Primary and sideport incisions
- Capsulorhexis
- Lens fragmentation

Use of any intraoperative power assessment is not permitted during surgery.

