4.1 Efficacy Endpoints

Primary Endpoint:

- Percentage of subjects not bothered at all by halos (on the QUVID questionnaire Q2.3) at 3 months post-implantation.

[figure not shown]
Secondary Endpoints:

- Percentage of subjects not bothered at all by glare (on the QUVID questionnaire Q3.3) at 3 months post-implantation.
- Percentage of subjects not bothered at all by starbursts (on the QUVID questionnaire Q1.3) at 3 months post-implantation.

[REDACTED]

[REDACTED]

- [REDACTED]
- [REDACTED]
- [REDACTED]
- [REDACTED]
- [REDACTED]
- [REDACTED]
- [REDACTED]
- [REDACTED]
- [REDACTED]
- [REDACTED]
- [REDACTED]
- [REDACTED]

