4.3.2 Secondary Effectiveness Analyses

For each comparator, if the primary effectiveness hypothesis is not successful, no hypothesis test for secondary effectiveness endpoints will be further conducted for that comparator. If the primary effectiveness hypothesis is successful, hypotheses for glare will first be tested. If the hypothesis for glare is successful, the hypothesis for starbursts will be tested.

The superiority hypothesis for each comparator will be evaluated using the Miettinen-Nurminen method (1985). The superiority hypothesis will be deemed supported if the lower limit of the two-sided 97.5% confidence interval exceeds zero. Main analysis will be based on AAS. [REDACTED]

Success on the secondary hypothesis tests, sequentially for glare then starbursts, will be concluded independently for between VIVITY and SYMFONY, and between VIVITY and AT LARA.

[REDACTED]

[REDACTED]

[REDACTED]

[REDACTED]

[REDACTED]

[REDACTED]

- [REDACTED]
- [REDACTED]
- [REDACTED]
- [REDACTED]

[REDACTED]

[Redacted text block]

[Redacted text block]

[Redacted text block]

[Redacted text block]

[Redacted text block]

[Redacted text block]

[Redacted text block]

4.3.3.6 % of Subjects Responding by Category to QUID Questionnaire Items (3 and 6 months)

For AAS, the number and percentages of subjects in each category of responses to each question on the QUID questionnaire will be reported by treatment group at each visit this questionnaire is administered.

[Redacted]

[Redacted]

[Redacted]

[Redacted]

[Redacted]

[Redacted]

[REDACTED]

[REDACTED]

[REDACTED]

[REDACTED]

[REDACTED]

[REDACTED]

[REDACTED]

[REDACTED]

[REDACTED]

[REDACTED]

- | [REDACTED]
- | [REDACTED]
- | [REDACTED]

[REDACTED]

[REDACTED]

[REDACTED]

[REDACTED]

[REDACTED]

[figure not shown]
[REDACTED]

[figure not shown]
[REDACTED]

Table 4-1 summarizes the key effectiveness analyses.

Table 4–1 Summary of Analysis Strategy for Key Effectiveness Endpoints

Endpoint	Main vs. Sensitivity Approach ^a	Statistical Method ^b	Analysis Set	Missing Data Approach
Primary				
Percentage of subjects not bothered at all by halo (on the QUID questionnaire Q2.3) at 3 months	M	Miettinen-Nurminen method	AAS	Observed data only
[REDACTED]	[REDACTED]	[REDACTED]	[REDACTED]	[REDACTED]
Secondary				
Percentage of subjects not bothered at all by glare (on the QUID questionnaire Q3.3) at 3 months	M	Miettinen-Nurminen method	AAS	Observed data only
[REDACTED]	[REDACTED]	[REDACTED]	[REDACTED]	[REDACTED]

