4.6 Handling of Missing Data

There be no imputation for missing data. The influence of missing data is expected to be minimal.

5 Safety Analysis Strategy

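### The superiority tests for halos, glare and starbursts should compare subjects by randomised lens, not by the lens actually implanted; separately, confirm that a missing-data sensitivity analysis exists.

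*SAP*

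**What the plan says.** **Grouping.** SAP 2.1 defines the primary effectiveness set: "AAS includes all randomized eyes with successful study IOL implantation". It then fixes how subjects are grouped: "All effectiveness analyses will be conducted according to actual IOL implanted". The sentence is complete and has no exception, although the text around it is redacted. The tested endpoints are at subject level; the primary one is "Percentage of subjects not bothered at all by halos (on the QUVID questionnaire Q2.3) at 3 months post-implantation" (SAP 4.1). The readable part of Protocol 12.2 defines the same set and gives no grouping rule. Protocol 9.3 says: "The lens to which the subject is randomized, must be implanted in both eyes".

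**Missing answers.** For all three tested endpoints, the main row of SAP Table 4-1 gives the missing-data approach as "Observed data only". SAP 4.6 adds: "There be no imputation for missing data. The influence of missing data is expected to be minimal". Table 4-1 also has a column headed "Main vs. Sensitivity Approach", and the row after each main row is redacted. The body of Protocol 12.5, on missing data, is not readable.

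**The concern.** The claim under test is a randomised superiority claim. Randomisation makes the groups as assigned comparable. It does not do that for groups formed by what happened in theatre. Allocation may take place up to 10 business days before the first surgery, and an unmasked site user is told the assignment (Protocol 9.4, SAP 1.3). A change of lens is therefore a post-randomisation event, and its cause may be related to the eye or to the subject's outlook. Grouping by lens received is usual for safety, and SAP 2.3 uses it there. For a superiority test it lets such an event move a subject from one side of the comparison to the other. The resulting error could favour either lens.

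The missing-data point is smaller. Whether a subject answers at Visit 4A could depend on the lens and on how bothered the subject is. An observed-only comparison therefore needs either a stated reason why this does not matter or a check. The readable part of SAP 4.6 states a conclusion without a reason.

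**Working it through.** **Inputs**
- Planned evaluable subjects: 60 per arm (Protocol 8, SAP 1.2).
- Significance level: SAP 4 splits 0.05 two-sided equally, 0.05 / 2 = 0.025 two-sided per comparator. This agrees with the one-sided 0.0125 in Protocol 12.4.1.2 and the 97.5% interval in SAP 4.3.1. The critical value is 2.2414.
- Success rule: lower limit of the Miettinen-Nurminen interval above zero (SAP 4.3.1, 4.3.2).
- Response counts: **assumed**, because no expected rate is readable.
- Number of wrong-lens cases: **assumed**, because no document gives an expected number.

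**Formula.** At a difference of zero the score statistic is

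z = (p1 - p2) / sqrt{ p(1 - p)(1/n1 + 1/n2) × N/(N - 1) }, with p the pooled proportion and N = n1 + n2.

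The lower limit exceeds zero exactly when z > 2.2414. The limit itself comes from inverting the same statistic over non-zero differences. A wrong-lens subject keeps the same answer; only the group in which that answer is counted changes.

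**One subject, comparator at 24/60.** For 36/60 v 24/60, p = 60/120 = 0.5, the standard error is sqrt(0.25 × 2/60 × 120/119) = 0.0917, and z = 0.200 / 0.0917 = 2.18, which is below 2.2414. The other rows follow in the same way.

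| Grouping | VIVITY v comparator | Difference (points) | z | Lower limit (points) | Test |
|---|---|---|---|---|---|
| As randomised | 36/60 v 24/60 | 20.00 | 2.18 | -0.55 | fails |
| As implanted: one bothered VIVITY-assigned subject received the comparator | 36/59 v 24/61 | 21.67 | 2.36 | +1.12 | succeeds |
| As randomised | 37/60 v 24/60 | 21.67 | 2.36 | +1.12 | succeeds |
| As implanted: one bothered comparator-assigned subject received VIVITY | 37/61 v 24/59 | 19.98 | 2.18 | -0.57 | fails |

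**Other assumed comparator rates.** Start one VIVITY subject short of significance as randomised, then count how many bothered VIVITY-assigned subjects must have received the comparator before the as-implanted test succeeds.

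| Comparator | VIVITY, one short | Lower limit | Cases needed | As-implanted counts | Lower limit |
|---|---|---|---|---|---|
| 15/60 | 26/60 | -1.17 | 2 | 26/58 v 15/62 | +1.14 |
| 20/60 | 32/60 | -0.36 | 1 | 32/59 v 20/61 | +1.09 |
| 24/60 | 36/60 | -0.55 | 1 | 36/59 v 24/61 | +1.12 |
| 30/60 | 42/60 | -0.13 | 1 | 42/59 v 30/61 | +1.88 |

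**A clear result.** In the first table one regrouped subject shifts the limit by 1.12 - (-0.55) = 1.67 or 1.12 - (-0.57) = 1.69 points. For 43/60 v 24/60 the limit is +11.41. At that rate, 11.41 / 1.69 = 6.75, so about seven regroupings, all in the same direction, would be needed to remove significance.

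**Missing answers.** No calculation is offered, because no readable text gives an expected number of missing Visit 4A answers in the AAS. Side by side, Table 4-1 uses observed data for the main analysis, SAP 4.6 rules out imputation and expects minimal influence, and the places where a sensitivity analysis would stand are redacted.

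**The case against.** **On grouping.** Protocol 9.3 requires the assigned lens in both eyes, Protocol 10.2.2 repeats it for surgery, and no readable text expects or permits anything else. With no wrong-lens case the two groupings are identical. The illustrations also sit at the significance threshold, where one subject can reverse any test; they show fragility there, not the size of a bias. All of this stands. It limits how much the point matters, but it does not justify the as-implanted rule for a superiority test. A reader might infer that the rule favours VIVITY, or that the SAP contradicts the protocol. The documents support neither: the effect runs both ways, and the readable protocol gives no grouping rule to contradict.

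**On missing data.** Three stronger readings are tempting, and none holds.
- *That no sensitivity analysis is planned.* The column headings of Table 4-1 and the redacted row after each main row suggest that one may exist. Redacted text cannot be counted as absent.
- *That the SAP predicts few missing answers.* It speaks of their influence, not their number.
- *That about six answers per arm will be missing, from (198 - 180) / 3 = 6.* Protocol 8 allows for "a 10% rate of subjects who are not bilaterally implanted with the study IOLs or are lost to follow-up". This pools two groups. Subjects never implanted are outside the AAS and so are not missing data within it. Completion runs to Visit 5A (days 120-180), whereas the tested answer is taken at Visit 4A (days 70-100), so a subject lost between the two still contributes. The figure is not an estimate of missing Visit 4A answers in the tested set.

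**Conclusion.** The grouping point holds on visible text: SAP 2.1 applies the lens implanted to every effectiveness analysis, including the three superiority tests. The expected effect is small. It is nil if every subject receives the assigned lens, and it can decide a test only when the result is borderline. There, under the assumed counts, one subject (two at the lowest comparator rate shown) is enough to reverse the conclusion, and the reversal can go either way. A result such as 43/60 v 24/60 would not be at risk from one or two cases. These figures rest on 60 per arm, on assumed response rates, and on the assumed answer of the subject who changes group.

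The missing-data point is secondary and is a request for confirmation. The readable text of SAP 4.6 gives no reason for expecting minimal influence. Whether the plan already contains a check cannot be determined from the public documents.

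**What to change.** 1. **SAP 2.1.** For the primary and secondary endpoints, replace the grouping sentence with: *The primary and secondary effectiveness analyses will group AAS subjects by randomised IOL; the analysis by actual IOL implanted will be supportive.* The cost is one extra supportive table, with no change to sample size, alpha or visits. If no wrong-lens case occurs, the main result is unchanged. This is not a full as-randomised analysis, because the AAS still excludes subjects who were never implanted, and the report should say so.

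2. **SAP 4.6.** Confirm that the redacted rows of Table 4-1 or Protocol 12.5 contain a missing-data sensitivity analysis for the Visit 4A answer. If they do, nothing need be added. Only if they do not, add a tipping-point table among AAS subjects with a missing Visit 4A answer, varying the assumed answers separately in each arm. In that case also amend 4.6 to say *no imputation in the main analysis*, so that the existing sentence does not contradict the new table. The cost is one table and needs no new data.

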2.3 Safety Analysis Set

The Safety Analysis Set (SAF) will include all eyes with attempted implantation (successful or aborted after contact with the eye). The SAF will be the primary set for all safety analyses.

All analyses at the eye-level endpoints (such as ocular adverse events) will be presented separately for first implanted eyes and second implanted eyes. While analyses at the subject-level endpoints (such as non-ocular adverse events) will be based on the subjects.

Safety analyses will be conducted using the safety analysis set on a treatment-emergent basis. For treatment-emergent safety analyses, eyes will be categorized under the actual IOL implanted (or attempted to implant).

3 Subject Characteristics and Study Conduct Summaries

Subject characteristics and study conduct summaries include tables and listings such as a subject disposition table, demographics and baseline characteristics tables (including age, gender, race), listing of treatment assignments by site, summary of screen failures by reason, and listing of subjects/eyes excluded from the analysis sets including reasons.

All summary statistics will be based on the type of variable. For categorical variables (eg, sex, race), summary statistics will include sample size, number in category, and % in each category. For continuous variables (eg, age, axial length), number of subjects/eyes, mean, median, standard deviation, minimum and maximum will be reported. Tables will be presented by treatment and overall.

[REDACTED]

[REDACTED]

[REDACTED]

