11 ADVERSE EVENTS AND DEVICE DEFICIENCIES

11.1 General Information

Note: AEs and device deficiencies must be recorded for all enrolled subjects from the time of signature of informed consent, regardless of subject enrollment status (screen failure or randomized).

An AE is any untoward medical occurrence, unintended disease or injury, or untoward clinical signs (including abnormal laboratory findings) in subjects, users, or other persons, whether or not related to the test article. Refer to the Glossary of Terms for categories of AEs and SAEs.

Figure 11-1 **Categorization of All Adverse Events**

[figure not shown]
[figure not shown]

Figure 11-2 Categorization of All Serious Adverse Events

[Redacted]

[Redacted]

[Redacted]

[Redacted]

[Redacted]

[Redacted]

[Redacted]

[Redacted]

[Redacted]

[Redacted]

[Redacted]

[Redacted]

Device Deficiencies

A device deficiency may or may not be associated with subject harm (ie, ADE or SADE); however, not all ADEs or SADEs are due to a device deficiency. The Investigator should determine the applicable category for the identified or suspect device deficiency and report any subject harm separately.

- [REDACTED]
- [REDACTED]
- [REDACTED]
- [REDACTED]
- [REDACTED]
- [REDACTED]
- [REDACTED]
- [REDACTED]

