12.2 Analysis Sets

The primary analysis set for effectiveness analyses will be the All-Implanted Analysis Set (AAS). AAS includes all eyes with successful study IOL implantation. [REDACTED]

[REDACTED]

[REDACTED]

[REDACTED]

[REDACTED]

[REDACTED]

[figure not shown]
Safety Analysis Set includes all eyes that had contact with a study IOL (successful or aborted implant).

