5.1 Safety Endpoints

Safety endpoints are:

- Adverse events including SSIs
- Device deficiencies
- IOP (clinically significant change)
- Slit lamp exam findings
- Dilated fundus exam findings
- IOL observations including IOL tilt/decentration
- Subjective PCO assessment
- Posterior capsulotomy
- Intraoperative surgical problems
- Other procedures at surgery (combined and/or additional).

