5.3 Statistical Methods for Safety Analyses

The focus of the safety analysis will be a comprehensive descriptive assessment of safety endpoints listed in Section 5.1. Except otherwise stated, the analysis set for all safety analyses is the safety analysis set as defined in Section 2.3. Baseline will be defined as the last measurement prior to exposure to investigational product, except otherwise stated.

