5.3.1 Adverse Events

The number and percentage of all ocular adverse events will be tabulated by preferred term with a breakdown by treatment, separately for first, second and all eyes. An eye with multiple ocular AEs of the same preferred term is only counted once toward the total of this preferred term.

Adverse events will be summarized in the following tables, by treatment group:

1. All Adverse Events (Serious and Non-Serious Combined)
 - a. Ocular
 - b. Nonocular

2. All Adverse Device Effects
 - a. Ocular
 - b. Nonocular

3. All Serious Adverse Events (including Serious Adverse Device Effects)
 - a. Ocular
 - b. Nonocular

3. Subject Listings
 - a. Non-serious Ocular
 - b. Non-serious Nonocular
 - c. Serious Ocular
 - b. Serious Nonocular

All ocular tables will be presented separately for first and second implanted eyes.

In addition, listings of adverse events will be provided. The listings will include the following variables: treatment, site, subject, eye, days from surgery, duration, adverse event description, causality, severity, seriousness, outcome and preferred term.

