5.3.11 Intraoperative Surgical Problems

Descriptive statistics (numbers and percentages) on eyes with surgical problems will be presented, separately for first and second implanted eyes.

In addition, a listing of subjects with surgical problems will be provided. The listing will include the following variables: treatment, site, subject, age, sex, eye, and description of surgical problem.

[figure not shown]
[figure not shown]

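### The safety set requires lens contact, so an eye stopped by a complication before the lens is introduced drops out of the surgical-problem rate

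*SAP*

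**What the plan says.** **Who is in the set.** SAP 2.3: "The Safety Analysis Set (SAF) will include all eyes with attempted implantation (successful or aborted after contact with the eye". Protocol 12.2 agrees in substance: "Safety Analysis Set includes all eyes that had contact with a study IOL (successful or aborted implant".

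**Where the set is used.** SAP 5.3: "Except otherwise stated, the analysis set for all safety analyses is the safety analysis set as defined in Section 2.3". SAP 2.3 adds a second restriction: "Safety analyses will be conducted using the safety analysis set on a treatment-emergent basis".

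**What is analysed on it.** SAP 5.1 names "Intraoperative surgical problems" among the safety endpoints. SAP 5.3.11 gives the analysis: "Descriptive statistics (numbers and percentages) on eyes with surgical problems will be presented, separately for first and second implanted eyes". For adverse events, SAP 5.3.1 states: "The number and percentage of all ocular adverse events will be tabulated by preferred term with a breakdown by treatment". Neither section, as far as it is visible, names another set. SAP 5.3.12 plans only a listing for other procedures at surgery.

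**What is collected.** Protocol 10.2.2 (steps 7 and 11) has problems and complications during surgery recorded, with no condition that a lens was introduced. Protocol 10.2.5 repeats this for the second eye. For adverse events, protocol 11.1 states: "AEs and device deficiencies must be recorded for all enrolled subjects from the time of signature of informed consent".

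**What else is planned.** SAP section 3 provides a listing of eyes left out of each analysis set, with the reason. SAP 3.1 tabulates and lists reasons for early discontinuation.

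**The concern.** An intraoperative problem is defined by surgery, and surgery begins before the lens is handled. The safety set is defined by a later step, contact with the lens. A complication during lens removal can be the very reason why that step is never reached. Whether an eye counts towards the surgical-problem rate then depends on the problem being counted, and the eyes removed are those whose problem was serious enough to stop implantation.

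The case is foreseeable. Protocol section 8 makes an allowance that includes subjects who do not receive study lenses in both eyes, and the protocol contents list a section (8.3) on reasons for not implanting.

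At stake is the accuracy of a descriptive safety rate in a study intended for publication. The same gap affects the ocular adverse event tables: such events are collected from consent, but those in operated eyes that no lens touched have no visible place in the planned summaries.

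**Working it through.** **1. Follow each kind of eye through the plan.**

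| What happens in the operated eye | Recorded (protocol 10.2.2, 11.1) | In safety set (SAP 2.3) | Place in the 5.3.11 rate |
|---|---|---|---|
| No problem, lens implanted | nothing to record | yes | denominator |
| Problem, lens implanted | yes | yes | numerator and denominator |
| Problem, lens introduced, then implantation aborted | yes | yes | numerator and denominator |
| Problem, surgery stopped before the lens is introduced | yes | no | neither |

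The last row is the gap. The same row applies to the ocular adverse event rates in 5.3.1.

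**2. Planned numbers (protocol section 8).** The documents plan 218 enrolled, 198 randomised and 180 completing, with two allowances of 10%. These reproduce as 180 × 1.10 = 198 and 198 × 1.10 = 217.8, rounded to 218. Dividing by 0.90 instead gives 200 and 220, a difference of two subjects that does not matter here. At 1:1:1, 198/3 = 66 randomised subjects per arm, hence about 66 first eyes per arm if surgery starts in all of them. First eyes are the right unit because 5.3.11 reports first and second eyes separately.

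**3. Effect on the rate.** Let n be the eyes in which surgery started, k those stopped by a complication before lens contact, and m the other eyes with a problem.

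- All operated eyes: (m + k)/n
- Safety set: m/(n − k)
- Difference: k(n − k − m)/[n(n − k)]

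Since m cannot exceed n − k, the difference is never negative. Such eyes can only lower the reported surgical-problem rate.

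With n = 66, and with k and m chosen for illustration:

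| k | m | All operated eyes | Safety set | Difference (percentage points) |
|---|---|---|---|---|
| 1 | 0 | 1/66 = 1.5% | 0/65 = 0.0% | 65/4290 = 1.5 |
| 1 | 2 | 3/66 = 4.5% | 2/65 = 3.1% | 63/4290 = 1.5 |
| 2 | 2 | 4/66 = 6.1% | 2/64 = 3.1% | 124/4224 = 2.9 |

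Each such eye moves a first-eye rate by about 1.5 percentage points.

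**4. How many eyes.** The documents give no rate of surgery stopped before lens contact. The 10% allowance combines non-implantation with loss to follow-up and cannot be split. Assume 0.5% to 3% of eyes. With at most 2 × 198 = 396 operated eyes, 0.005 × 396 = 1.98 and 0.03 × 396 = 11.88, so about 2 to 12 eyes over the three arms.

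**5. Adverse events.** For a preferred term that such an eye experienced, the arithmetic of step 3 applies. For any other term only the denominator changes, for example 2/65 = 3.1% against 2/66 = 3.0%, which is negligible. The one-directional argument therefore belongs to the surgical-problem rate and to the terms describing the complication itself.

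**The case against.** **An exposure-based safety set is sound for a lens comparison.** A complication that precedes the lens cannot be caused by it, and the rate among exposed eyes is a valid figure for exposed eyes. This stands for lens-attributable endpoints, and the set should be kept for them. It does not answer the point for an endpoint defined by the operation, or for a table meant to hold all adverse events.

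**The eye does not vanish.** The listing of excluded eyes with reasons would show it. Non-ocular events are analysed by subject, so a subject whose other eye is in the set presumably remains. Serious events are reported to the sponsor regardless of the set. It is also arguable whether the default in SAP 5.3 governs raw listings. All this stands as partial visibility. It does not put the eye back into the rate, and the exclusion listing is not specified to report its events.

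**The text is incomplete.** The body of protocol 8.3 is not visible, parts of the safety sections are blacked out, and the table shells named in the SAP are not available. A provision for these eyes cannot be ruled out. Still, 5.3.11 can be read and names no other set.

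**A reader might infer more than the documents support.**

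- *Bias between lenses.* Assignment is known to unmasked site staff before surgery and the lenses differ in design, so one might suppose that the threshold for not proceeding differs by arm. Nothing in the documents says or shows that.
- *A biased rate for other procedures at surgery.* SAP 5.3.12 plans a listing only, so there is no rate to distort.
- *A pooled rate over both eyes.* SAP 5.3.11 does not plan one, so a two-eye denominator would misdescribe what is reported.

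**Conclusion.** The point holds in a limited form. On the visible text, an eye whose surgery is stopped by a complication before the lens is introduced is recorded, but is left out of the intraoperative-problem rate and the ocular adverse event rates. For the surgical-problem rate the exclusion depends on the outcome and works in one direction.

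The size is about 1.5 percentage points per such eye in a first-eye group of 66. How often this occurs is unknown. The range of 2 to 12 eyes rests wholly on an assumed 0.5% to 3%, and the number could be nil. The effect is probably small. There are no safety hypotheses, and neither the primary endpoint nor study success is touched. The reason to act is that the correction is cheap. The conclusion assumes that no redacted passage or table shell already covers these eyes.

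**What to change.** 1. In SAP 5.3.11, summarise all eyes of randomised subjects in which study surgery was started, separately for first and second operated eyes. Group by the assigned lens where no lens was introduced.
2. In SAP 5.3.1, do the same for ocular adverse events with onset on the day of surgery. State that both summaries are exceptions to the default set in 5.3 and to the treatment-emergent restriction in 2.3.
3. State that the 5.3.12 listing covers the same eyes.
4. Add one listing of adverse events in enrolled subjects or eyes outside the safety set.
5. Keep the contact-based set for lens-exposure endpoints.

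The cost is SAP wording and one listing, with no new data collection. The downside is that the reported surgical-problem rate may be slightly less favourable.
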